8.3.1.2 Seizure-free days

The number of seizure-free days will be the total number of days within an interval for which daily diary data was available and indicated that no seizures occurred. The percentage of seizure-free days will be computed as 100 times the number of seizure-free days divided by the number of days for which daily diary data was available. Days without the corresponding daily diary data will not be used in these computations.

8.3.1.3 Seizure Severity Global Item (SSG) variables

The SSG consists of 1 item at baseline or 2 items during follow up from the Seizure Severity Questionnaire and asks the subjects to evaluate the severity of their seizures for the last 4 weeks and/or since the Baseline. The subject describes all seizure types when answering the questions.

The SSG is completed according to the schedule of study procedures in Table 2-2 (Visits 2, 4, 7 and 9) and is provided to each subject at the beginning of the visit. The SSG data are collected on 2 separate CRFs. On the "Seizure Severity Global Item – Baseline", seizure-intensity during the

last 4 weeks is collected on a 7-point scale with 7 = very severe; On the “Seizure Severity Global Item – Follow-up” CRF, seizure-intensity during last 4 weeks is collected on a 7-point scale with 7 as very severe. Assessment of change since starting IMP, is also collected on a 7-point scale with 7 = much worse.

8.3.1.4 QOLIE-31-P variables

The QOLIE-31-P assesses subject functioning and health-related quality of life. The QOLIE-31-P (Cramer et al, 2003) is an adaptation of the original QOLIE-31 instrument (Cramer et al, 1998) that includes 31 items grouped into 7 multi item subscales (Seizure Worry [5 items], Overall Quality of Life [2 items], Emotional Well-being [5 items], Energy/Fatigue [4 items], Cognitive Functioning [6 items], Medication Effects [3 items], and Daily Activities/Social Functioning [5 items]) and 1 health status item.

In addition to the 31 items of the QOLIE-31, the QOLIE-31-P contains 7 items assessing the degree of “distress” associated with the topic of each subscale (ie, distress items) and 1 item asking about the relative importance of each subscale topic (ie, prioritization item).

The QOLIE-31-P will be completed according to the schedule of study procedures in Table 2-2 (Visits 2, 4, 7 and 9) and is provided to each subject at the beginning of the visit. The subject completes the questionnaire on his/her own. The Investigator or designee will verify that all questions have been answered. Further details about the QOLIE-31-P are provided in the scoring manual.

8.3.1.5 Hospital Anxiety and Depression Scale (HADS) score variables

The HADS is administered at Visits 2, 4, 7 and 9. The HADS scores for anxiety and for depression range from 0-21 with higher scores indicating a worse state. A score below 8 is considered to be normal (Zigmond and Snaith, 1983). HADS subscale scores will be determined by summing the scores of the 7 items belonging to each of the two subscales, i.e. anxiety (odd numbered questions) and depression (even numbered questions). The following rules will be applied for the computation of the subscale scores: 1) Missing items values will be set to the mean score of the subscale to which the item belongs, provided 50% or more of the items within the subscale are present. 2) The subscale scores will be calculated if 50% or more of the items within a subscale are present.

8.3.2 Analysis of other efficacy variables

Other efficacy variables and tests will be carried out at a nominal two-sided 0.05 significance level and no multiplicity adjustments will be applied.

8.3.2.1 The 50% responder rate over the 16-week Treatment Period

The 50% responder rate during the entire 16-week Treatment Period will be listed, for the RS.

8.3.2.2 The 75% responder rate over the 16-week Treatment Period

The 75% responder rate during the entire 16-week Treatment Period will be listed, for the RS.

8.3.2.3 The 90% and 100% responder rates over the 12-week Maintenance Period

The 90% and 100% responder rates during the 12-week Maintenance Period will be listed for the RS.

8.3.2.4 Percent reduction in observable focal-onset seizure frequency from Baseline, over the 16-week Treatment Period

The same methodology described in Section 8.2.1.3 will be applied.

8.3.2.5 The 50% responder rate status for focal-onset (Type I) seizures over the 12-week Maintenance Period

The 50% responder rate for Type I focal-onset seizures during the 12-week Maintenance Period will be listed for the RS.

8.3.2.6 The 75% responder rate for focal onset (Type I) seizures over the 12-week Maintenance Period

The 75% responder rate for Type I focal-onset seizures during the 12-week Maintenance Period will be listed for the RS.

8.3.2.7 The 90% and 100% responder rates for focal-onset (Type I) seizures over the 12-week Maintenance Period

The 90% and 100% responder rates for Type I focal-onset seizures during the 12-week Maintenance Period will be listed for the RS.

8.3.2.8 Percent reduction in focal-onset (Type I) seizure frequency from Baseline, over the 12-week Maintenance Period and the 16-week Treatment Period

Percent reduction in focal-onset (Type I) seizure frequency from baseline over the 12-week Maintenance Period and the 16-week Treatment Period will be listed.

8.3.2.9 The 50% responder rate for Type IA1, IB, or IC seizure over the 12-week Maintenance Period

50% responder rate in Type IA1, IB, or IC seizure over the 12-week Maintenance Period by each seizure type separately will be listed for the RS.

8.3.2.10 The 75% responder rate for Type IA1, IB, or IC seizure over the 12-week Maintenance Period

75% responder rate in Type IA1, IB, or IC seizure over the 12-week Maintenance Period by each seizure type separately will be listed for the RS.

8.3.2.11 Percent reduction in Type IA1, IB, or IC seizure frequency from Baseline, over the 12-week Maintenance Period and the 16-week Treatment Period

Percent reduction in Type IA1, IB, or IC seizure frequency from baseline over the 12-week Maintenance Period and the 16-week Treatment Period will be listed.

8.3.2.12 Seizure-freedom status (yes/no) during the 12-week Maintenance and the 16-week Treatment Period

Seizure freedom status will be evaluated for each treatment by summarizing the percentage of seizure-free subjects as a response rate during the 12-week Maintenance Period and during the entire 16-week Treatment Period. The seizure freedom rate will be calculated based on the Completer Set. The seizure freedom rate for each of these periods will be analyzed using an exact conditional logistic regression model where treatment group is included in the model and region and Baseline SV2A use are included as strata.

8.3.2.13 Percentage of seizure-free days during the 12-week Maintenance Period and the 16-week Treatment Period

The percentage of seizure-free days during the Maintenance Period and Treatment Period will be listed. The change in the percentage of seizure-free days from the Baseline Period to the Maintenance Period and Treatment Period will also be listed.

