### **13.3 Planned efficacy/outcome analyses**

The efficacy variables will be analyzed as described below using the FAS.

Total seizure frequency per 28 days will be derived from the seizure count information recorded on the diary card and is defined as the number of seizures standardized to a 28-day period. It is computed as the number of seizures recorded over a period, divided by the total number of days in that period, multiplied by 28. Observable focal-onset seizures refers to Type IA1, IB, and IC seizures (according to the ILAE Classification of Epileptic Seizures, 1981). Focal-onset seizures include all Type I seizures. Seizure-free status and seizure-free days include all (Type I, II, and III) seizure types.

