### **13.3.3 Other efficacy analyses (this applies for all regulatory authorities)**

All other analyses of the 75% and 50% responder rate endpoints will be analyzed using the same logistic regression model as specified in Section 13.3.1.2. Analyses of 90% responder rate and seizure freedom will use the same methodology. In addition to observable focal-onset seizures and focal-onset seizures, analyses will also be carried out on all seizures (seizure-free status and seizure-free days) during the 12-week Maintenance Period and the 16-week Treatment Period.

All other analyses of the change from Baseline in seizure frequency will be analyzed using the ANCOVA model on the log-transformed data, as specified in Section 13.3.1.1.

The time-to-return to Baseline observable focal-onset seizure frequency will be analyzed using Kaplan-Meier methodology. Additional details of the analysis will be captured in the SAP.

The QOLIE-31-P and SSG assessments will be summarized using descriptive statistics by each available visit.

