3.2.3 Analysis periods

The start and end dates of each analysis period (following the study design) are used for the classification of efficacy and safety data. The exact start and end of each of these periods is described for calculation purposes in [Table 3-1: Start and end of EP0092 analysis periods](#). Note that measurements obtained from diaries returned on the start date of the Titration and Stabilization Period would be included in the Baseline Period calculations. Refer to [section 3.3.1](#). Similarly, measurements from diaries returned on the start date of a subsequent period would be included in calculations for the previous period.

Table 3–1: Start and end of EP0092 analysis periods

Analysis Period			Details
Description	Start	End	
Baseline (Week -4)	Date of informed consent at Visit 1	Date of the day before the date of Visit 2.	This is an approximate 28-day period for calculation of Baseline seizure frequencies. Study drug is dispensed, and first dose is generally taken the day of the Baseline Visit (Visit 2, Day 1). Note the pre-dose assessments will also be included in the Baseline Period.
Titration and Stabilization*	The date of the Baseline Visit, (Visit 2, Day 1).	The date of the day before Visit 4 or the end of the treatment period if the subject has discontinued prior to Visit 4.	For evaluation purposes, if results are presented by analysis period, the Titration and the Stabilization interval will be considered together (approximately 4 weeks in total). Titration is a period of dose increases to reach the protocol specified dose. Stabilization is an approximate week-long interval to stabilize at the target dose level. During stabilization the dose may be adjusted once (i.e. to a fallback dose).
Maintenance*	The date of Visit 4.	The date of Visit 7 or the end of the treatment period if the subject has discontinued prior to Visit 7.	This is a 12-week period where the subject remains on the randomized target dose (or fallback dose, if applicable).
16-week Treatment Period*	The date of the Baseline visit (Visit 2)	The date of Visit 7 or the end of the treatment period if the subject has discontinued prior to Visit 7.	Titration and Stabilization Period and Maintenance Period combined.
Conversion	The date of the day after Visit 7	The date of Visit 8.	This is a 3-week period of dose conversion to enable the subjects to enroll into the OLE study EP0093.

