3.5.6 Completer Set

The Completer Set is a subset of the FAS, consisting of those subjects who completed the 16-week treatment period.

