3.9 Changes to protocol-defined analyses

Due to Covid-19 impact on site initiation and enrollment and due to early termination of the study, the following items in the protocol were updated in this SAP.

Section in this SAP	Description	Change from the protocol
2.2	Efficacy variables	Removed: Seizure-free days
2.2.3	Other efficacy variables	Removed: Time to return to baseline 28-day observable focal-onset seizure count during the 12 week Maintenance Period
Table 2-1:	Schedule of Assessments	Added Setting (Required Onsite) column to include data that may be collected through phone or video calls for visit, during the pandemic.
3.5.5	Per Protocol Set	Due to early termination of the study, PPS will not be included in the study. Removed: The Per Protocol Set (PPS) is a subset of the FAS, consisting of those subjects who had at least 1 post-Baseline efficacy measurement and who had no major protocol deviation affecting the primary efficacy variable, as confirmed during a pre-analysis data review meeting, conducted prior to study unblinding.
3.10	COVID-19 eCRF	Added, see section 3.10 for details

4.3.1	Sequential Analyses	Removed all text associated with China region due to no patient enrollment and due to early termination of the study.
4.8	Examination of subgroups	Removed: subgroup by region, gender, age Added: Levetiracetam/Brivaracetam use at study entry (Y/N) based on AED medication CRF.
6.2	Other Baseline characteristics	Removed text associated with China region.
8.1.2.2	Supportive and sensitivity analyses for the primary variable for submission to the US FDA, PMDA, and other regulatory authorities not referencing EMA	Removed text related to sensitivity analyses due to changed scope of the study.
8.1.2.4	Supportive and sensitivity analyses for the primary variable for submission to the EMA and regulatory authorities who reference EMA.	Removed text related to sensitivity analyses due to changed scope of the study.
8.1.3	Analysis of primary efficacy variable for submission to the CFDA	Removed text associated with China region.

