4.6 Use of an efficacy subset of subjects

The FAS will be used for the primary efficacy analyses. No other efficacy subsets are defined for statistical analyses.

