8.3.1.1 Seizure-freedom status (Yes/No)

A subject is defined as seizure free (ie, seizure-freedom status=Yes) during a specific evaluation period if they meet all of the following criteria:

1. The subject completed the specific time period.
2. The subject did not have any missing diary days over the time period. Missing diary day refers to no diary available at all for that day. If the diary for the day is present and 'no seizures' is checked then the diary day is not missing.
3. The subject did not report any seizure of any type over the time period.

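### Seizure freedom is tested on completers only, although non-completers already count as not seizure free; the SAP contradicts itself and departs from the protocol without listing the change

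*SAP*

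**What the plan says.** SAP 8.3.2.12 covers seizure freedom over the 12-week Maintenance Period and the 16-week Treatment Period. It fixes the denominator: "The seizure freedom rate will be calculated based on the Completer Set". The same paragraph analyzes the rate by exact conditional logistic regression, with treatment in the model and region and Baseline SV2A use as strata.

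Four other SAP passages and two protocol passages bear on this:

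- SAP 3.5.6 defines the set: "The Completer Set is a subset of the FAS, consisting of those subjects who completed the 16-week treatment period".
- SAP 8.3.1.1 lists what a subject must meet to be seizure free. The first criterion is "The subject completed the specific time period".
- SAP 3.2.3, Table 3-1, gives Maintenance and the 16-week Treatment Period the same end: "The date of Visit 7 or the end of the treatment period if the subject has discontinued prior to Visit 7".
- SAP 4.6 names the FAS for the primary efficacy analyses and adds: "No other efficacy subsets are defined for statistical analyses".
- Protocol 13.3: "The efficacy variables will be analyzed as described below using the FAS".
- Protocol 13.3.3, which sits under 13.3, refers back to the responder-rate logistic regression: "Analyses of 90% responder rate and seizure freedom will use the same methodology".

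SAP 3.9 introduces its table of departures by saying that "the following items in the protocol were updated in this SAP". The table has no row for section 3.5.6 or 8.3.2.12.

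**The concern.** Completion is known only after randomization and can depend on treatment. Restricting a between-arm test to completers mixes any effect on seizures with differences in who stays in the study.

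The restriction also adds nothing to the endpoint definition. A non-completer is already classified as not seizure free, so the only effect is to take those failures out of the denominator.

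Either arm could lose more subjects. Protocol 2.3.1 says adverse events on PSL tend to be dose-related, which could mean fewer PSL completers. Protocol 6.3, criterion 6, withdraws subjects whose seizures worsen seriously, which could mean fewer placebo completers.

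Amendment 1 of the SAP reduced most 'other' efficacy variables to listings. Seizure freedom is one of the few that keeps a between-group test, so the population for that test should be the randomized one, or the departure should be stated.

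**Working it through.** **Plan's own figure.** The documents give no expected seizure-freedom rate for this trial and no completion rate by arm, so there is nothing to reproduce. The planned size is 100 per arm (protocol 13.8, SAP 2.6). Protocol 5.4.1 cites a 1% to 4% chance of complete seizure control with another regimen after four or more. I use that only as a rough guide to the event rate.

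**Step 1: the numerator does not change.** Seizure free requires completing the period (8.3.1.1). Completing Maintenance means reaching Visit 7, which also completes the Treatment Period (Table 3-1). Every seizure-free subject is therefore in the Completer Set.

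**Step 2: effect on the rate.** Let S be the seizure-free count, N the FAS size and d the proportion not completing.

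- FAS rate = S/N.
- Completer Set rate = S/[N(1 − d)] = FAS rate/(1 − d).
- The PSL/placebo rate ratio is multiplied by (1 − d_placebo)/(1 − d_PSL).

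A zero rate stays zero. The risk difference need not move the same way: with 5 versus 1 seizure free out of 100 and non-completion of 10% versus 30%, it goes from 4.0 points to 5/90 − 1/70 = 4.1 points, in favor of the arm that lost fewer.

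**Step 3: what happens with no true effect.** Assume d = 10% on placebo and 25% or 35% on PSL. Let non-completers be r times as likely as completers to have been seizure free had they stayed, with equal overall rates in the arms. Each arm's completer rate is then proportional to 1/[(1 − d) + d·r], and the FAS ratio is the Completer Set ratio × (1 − d_PSL)/(1 − d_placebo).

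| r | Completer Set ratio (25% / 35%) | FAS ratio (25% / 35%) |
|---|---|---|
| 1 (dropout unrelated to seizures) | 1.00 / 1.00 | 0.83 / 0.72 |
| 0.5 | 1.09 / 1.15 | 0.90 / 0.83 |
| 0 (all would have failed) | 0.90/0.75 = 1.20; 0.90/0.65 = 1.38 | 1.00 / 1.00 |

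If placebo loses more instead, the Completer Set ratios are the reciprocals, from 1.00 down to 0.83–0.72.

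For r = 0 the spurious gap at a 4% rate is 5.33–6.15% against 4.44%, or 0.89–1.71 points. At a 1% rate it is 1.33–1.54% against 1.11%, or 0.22–0.43 points. For r = 1 it is zero.

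**Step 4: effect on the test.** Two-sided Fisher exact test at 0.05, standing in for the stratified exact model, at a 4% rate and no true effect:

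| Subjects per arm (completers: placebo vs PSL) | r = 0: rejected (toward PSL) | r = 1: rejected (toward PSL) | FAS, equal FAS rates |
|---|---|---|---|
| 100 (90 vs 75) | 4.30% (3.57%) | 3.05% (1.90%) | 1.68% |
| 100 (90 vs 65) | 5.29% (4.79%) | 2.68% (1.41%) | 1.68% |
| 50 (45 vs 38) | 2.43% (2.22%) | 1.34% (1.14%) | 0.42% |
| 50 (45 vs 32) | 2.50% (2.31%) | 0.89% (0.65%) | 0.42% |

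For r = 0.5 at 100 per arm, rejection is 3.26–3.45%, of which 2.36–2.50% is toward PSL. The 50 per arm is assumed, because the study ended early and the achieved size is not given. At a 1% rate, r = 0 rejection is at most 0.7% (100 per arm) or 0.1% (50 per arm).

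**Step 5: a single data set.** With 2/100 versus 8/100 seizure free, Fisher p = 0.10 on the FAS. On completers it is 0.022 for 2/90 versus 8/70, and 0.19 for 2/70 versus 8/90. The choice of set can move a nominal result either way.

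**The case against.** The case for leaving the text alone has four parts.

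- **The exception is stated.** SAP 8 makes the FAS the default unless a section says otherwise, and 8.3.2.12 does say otherwise. SAP 15.1, Change #5, logs the new set. This stands: the use is not hidden. It does not remove the literal contradiction with 4.6 or supply the missing row in 3.9.
- **Protocol 13.3.3 names a method, not an analysis set.** Correct. The conflict over the set is with 13.3, under which 13.3.3 falls. The direct mismatch with 13.3.3 is the model: the protocol points to the 13.3.1.2 logistic regression, which includes Baseline seizure frequency, while the SAP uses exact conditional regression without it. That change has no row in 3.9 either.
- **The FAS can be the tilted set.** If dropout is unrelated to seizures, the Completer Set ratio is 1.00 and the FAS ratio 0.83–0.72. FAS rejection is then about 0.2–0.3% toward PSL and 1.2–1.7% toward placebo at a 4% rate and 100 per arm. With true completer rates assumed at 4% versus 14%, power is 55–60% on completers and 26–38% on the FAS. Early termination makes some administrative dropout plausible. This stands as a real trade-off, and it is why both rates should be shown.
- **The distortion is small and assumed.** Rejection toward PSL clearly exceeds 2.5% only when every non-completer would have failed and the full 100 per arm was reached. This also stands.

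**Conclusion.** The concern holds and is minor. That the numerator is unchanged and only failures leave the denominator follows from the SAP's own definitions and needs no assumption. The conflicts with SAP 4.6 and protocol 13.3, and the gap in SAP 3.9, are plain on the page.

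The size and direction of any distortion between arms cannot be determined. They rest on assumed dropout, an assumed link between dropout and seizures, and an event rate borrowed from the protocol's background text. Within an arm, the rate can only rise or stay the same.

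The practical consequence is limited. The variable is tested at nominal 0.05, outside the Hochberg procedure, and few events are expected: at a 1% rate an arm has a 37% chance (n = 100) or 61% chance (n = 50) of no seizure-free subject at all. A reader can recover the FAS rate from the count and the FAS size, but no FAS test is planned.

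**What to change.** Replace the analysis-set sentence in SAP 8.3.2.12 with:

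> Seizure freedom will be calculated and tested on the FAS. Subjects who did not complete the period count as not seizure free (Section 8.3.1.1). The Completer Set rate will be shown as a labelled descriptive supplement, without a test. The number of FAS subjects who did not complete because the sponsor ended the study will be shown by treatment group.

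In 4.6, say that the Completer Set is used only for this descriptive rate. In 3.9, add a row for the Completer Set, and record there the change from the protocol's logistic regression to exact conditional regression without Baseline seizure frequency.

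The cost is one paragraph, one sentence, one table row, a changed denominator and one count by arm. SAP 5.1 already collects the primary reason for premature termination. The CRF list is not shown, so check that it separates sponsor termination.

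The downside is that non-zero rates will be lower, subjects stopped only because the study ended will count as failures, and an arm with more dropout unrelated to seizures will look worse. The supplementary rate and the termination count let the reader see how far that matters.

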8.3.2.14 Change in the SSG score

All data will be listed by subject for Baseline and at each scheduled assessment visit for each of the 7 categories of change (much better through much worse).

8.3.2.15 Change in the QOLIE-31-P score

The scoring algorithm for QOLIE-31-P is described in Section 8.3.1.3. Observed values and change from Baseline for QOLIE-31-P total score and subscale scores for Seizure Worry, Daily Activities/Social Function, Energy/Fatigue, Emotional Well-Being, Cognitive Function, Medication Effects, Overall Quality of Life, Health Status will be listed by subject.

